6.5. POOLING OF CENTERS

Subjects will not be pooled based on site size, but rather by region, to ensure a sufficient number of subjects per treatment arm in both the ITT and PP sets for analysis that contain region as a model effect. The tables below show which countries comprise each of the regions to be used in analysis.

Region	Country
Europe	France
	Spain
North America	United States
Asia	Japan

7. DEMOGRAPHIC, OTHER BASELINE CHARACTERISTICS AND MEDICATION

7.1. SUBJECT DISPOSITION AND WITHDRAWALS

Subject disposition data will be listed. A disposition table will present, by treatment group and overall, the number and/or percentage of subjects who signed the informed consent and entered the study (i.e., were screened, screen failed prior to Run-in, screen failed during the Run-in, and randomized), complete the study drug, discontinued study drug, completed the study, and discontinued from the study after randomization. The reasons for early withdrawal after randomization will be summarized.

Assignment to the analysis sets (Safety, ITT, and PP) will be summarized.

7.2. SUBJECT ELIGIBILITY AND PROTOCOL DEVIATIONS

All subjects, including screen failure subjects, who violate the Inclusion/ exclusion criteria will be listed. Reason for screen failure will be summarized.

Deviations that could affect the primary and secondary variables will be considered when determining a subject's eligibility for the PP Analysis Set. The number and percent of subjects who had any major deviation and each type of major protocol deviation will be tabulated for the ITT Analysis Set. All deviation term and class will be listed.

7.3. DEMOGRAPHIC AND OTHER BASELINE CHARACTERISTICS

Demographic characteristics include age, gender, race, ethnicity, and country and region of investigational site. Baseline characteristics will include baseline HbA1c values, blood pressure, height, body weight, BMI, FPG, eGFR, eGFR baseline groups (<45 or ≥45 mL/min/1.73m²), UACR, duration of diabetes from diagnosis to the date of informed consent, and prior anti-diabetic treatment status at screening. Baseline will be defined as the last non-missing value prior to randomization. Randomization stratification related factors will be summarized based on data collected on CRF or by lab. They include screening HbA1c groups (7.0 to 8.5% vs. 8.6 to 10.5%), screening anti-diabetic treatment status (insulin treated, other), screening eGFR values, and screening eGFR groups (30-44 or 45-59 mL/min/1.73m²). Stratification factors from IWRS will be summarized if they are not consistent with CRF or lab values. Summary descriptive statistics by treatment will include counts and percentages for discrete variables and estimation of means, standard deviations, medians, inter-quartile range (Q1, Q3), minimum, and maximum for continuous variables. Subjects' baseline

demographic and personal baseline characteristics will be summarized by treatment group and overall for subjects in the Safety, ITT, and PP Analysis Set. Subject age will be the age at date of informed consent collected from CRF.

Demographics data and randomization stratification factors will be presented in a data listing. Prior treatment will be listed along with all medications.

7.4. MEDICAL HISTORY

Significant medical and surgical history, including dates of diagnoses and procedures and whether the condition is ongoing, if applicable, will be collected. Each condition will be recorded as a verbatim term, date of onset, date resolved, and a checkbox that indicates ongoing conditions. Significant surgical and medical history will be coded using the Medical Dictionary for Regulatory Activities (MedDRA) Version 19.0 or higher.

Medical and surgical history will be summarized for the Safety Analysis Set by treatment group, system organ class (SOC), and MedDRA preferred term (PT), overall. Subject data will be listed.

Subject renal, diabetes and cardiovascular diseases history will be summarized for all categorical variables by frequency and percentage. Listing will be provided.

7.5. MEDICATION

All prescription and over-the-counter medications, including vitamins and herbal supplements, that subjects receive during the trial must be documented on the CRF. The medication name, dose, frequency, route of administration, date(s) of administration and reason for administration must be recorded. This documentation should continue through the treatment period and the follow up period.

All medication will be coded using the World Health Organization Drug Dictionary (WHO-DD) version March 2016 or higher. Preferred drug name, Anatomical/Therapeutic/ Chemical (ATC) class will be reported for inclusion in the database.

Medication summaries based on ATC level 2 and the preferred drug names will be produced for the Safety Analysis Set. The summaries will present, by treatment group, the frequency and percentage of subjects who used any medication in an ATC class, or any medication based on a single preferred drug name. Medication summaries will be sorted by descending total frequency of ATC class and by PT within ATC class. Subjects will be counted only once for each medication class and each preferred drug name.

For subject listings, medications will be reported based on ATC class and PT; multiple medications for an individual subject will be listed by start date and then by stop date, from earliest to latest medications.

7.5.1. Prior Medication

Any medication with a start date prior to or on first dose date for the double-blind treatment period will be considered a prior medication. If the entire start date of a given medication is missing, then the medication will be considered as prior medication.

No summary for prior medication will be presented. Prior and concomitant medications will be presented together on a single listing. The listing will be ordered by subject number and medication start/end dates. Prior medication will be flagged.

7.5.2. Concomitant Medication

A concomitant medication is any medication that starts prior to double-blind treatment period and continue into double-blind treatment period, or started after the first dose of double-blind treatment. All medications or treatment for controlling hyperglycemia will be recorded as concomitant medications in CRF. In the case of completely missing stop date, medication will be assumed to be concomitant.

Concomitant medications will be presented in a summary table as well as in a subject listing.

7.5.3. Rescue Medication

Rescue medication is any new anti-hyperglycemic medication that a subject starts taking during the double-blind treatment period or an increase in dose of the anti-hyperglycemic medication that the subject has been taking and continued for more than 2 weeks. Rescue medications will be summarized in a separate table and flagged in the same listing.

Independent blinded medical reviewers will identify the rescue medication before the study is unblinded. Adjudication process and definition of dose intensification and relaxation will be specified in a separate adjudication plan (Appendix 21.1).

8. EFFICACY

Efficacy data include HbA1c, FPG, body weight, SBP, DBP, and albuminuria.

8.1. PRIMARY EFFICACY ENDPOINT AND ANALYSIS

The primary efficacy hypothesis is that bexagliflozin reduces HbA1c after 24 weeks of treatment when compared to placebo.

8.1.1. Primary Efficacy Analysis

Let $\mu_{\text{Bexagliflozin}}$ and μ_{PBO} represent the mean changes from baseline in HbA1c at Week 24 for bexagliflozin and placebo arms, respectively. The following hypotheses will be tested:

$$H_0: \mu_{\text{Bexagliflozin}} = \mu_{\text{PBO}} \text{ versus } H_1: \mu_{\text{Bexagliflozin}} \neq \mu_{\text{PBO}}$$

This hypothesis will be tested based on ITT analysis set using all observed data and a mixed model repeated measures (MMRM) approach. Treatment, visit, treatment-by-visit, region, screening anti-diabetic treatment regimen (insulin treated or other), baseline eGFR (<45 or ≥ 45 mL/min/1.73m²) will be applied as fixed effects. Baseline HbA1c will be used as covariate. The analysis will evaluate the mean change from baseline in HbA1c over the 24-week double-blind treatment period. An unstructured covariance will be used to model the within-subject correlation. The Kenward-Roger approximation will be used to estimate denominator degrees of freedom. If the model with the unstructured covariance structure does not converge, an autoregressive (1) covariance structure will be used. HbA1c values obtained after the start of rescue medication will not be excluded from the analysis.

Based on the MMRM model, the treatment and treatment-by-visit interaction terms allow for comparisons of the treatment groups at each visit. Least squares (LS) mean treatment differences between the bexagliflozin group and the placebo group at week 24 will be estimated from the model with the corresponding p-values and their two-sided 95 % CIs presented. Sample SAS code will be provided in Appendix 21.2.

Descriptive statistics (n, mean, Q1, median, Q3, SD, minimum, and maximum) will be reported by treatment group and visit, along with the least squares means, differences between LS means, a 2-sided 95% confidence interval for each difference, p-values from the model effects. In addition, the LS means with standard errors of the change from baseline over time and difference between treatment groups with 95% will be presented graphically for the ITT Analysis Set.

For supportive analyses, the primary efficacy endpoint will be analyzed with observed available data using the PP analysis set in a similar manner as above. LS means over time will also be presented graphically.

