3.7. DETERMINATION OF SAMPLE SIZE

Approximately 300 subjects will be randomized and equally allocated to receive bexagliflozin tablets, 20 mg, or placebo.

The sample size calculation for this study is based on a two group t-test with a two-sided significance at the 5% level and the following assumptions:

- 1) The placebo-corrected population mean change from baseline to Week 24 in HbA1c in the dose group of 20 mg will be -0.4%.
- 2) The pooled standard deviation for the change from baseline to Week 24 in HbA1c for the active and placebo groups will be 1.0%.

Under the above assumptions, an estimated sample size of 133 evaluable subjects per treatment arm yields approximately 90% power to detect a treatment difference between bexagliflozin and placebo. A sample size of 150 per arm has been selected to account for a potential 12% drop-out and to allow adequate safety evaluation. The total sample size for this study will be 300 subjects.

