8.2.1. Key secondary efficacy endpoints and analyses

The primary superiority test on lowering of HbA1c at week 24 from baseline for bexagliflozin when compared to placebo will be conducted at 0.05 significance level. If it is significant, the hierarchical testing strategy will be followed to preserve experiment-wide type I error of 0.05. The key secondary efficacy end points will be tested in the order:

1. Superiority test of the change in body weight in subjects with baseline BMI ≥ 25 kg/m² at week 24 in the bexagliflozin group compared to the placebo group
2. Superiority test of the change in systolic blood pressure (SBP) over time in subjects with SBP ≥ 130 mmHg in the bexagliflozin group compared to the placebo group
3. Superiority test of the change in HbA1c at week 24 in subjects with eGFR 45 to 59 mL/min/1.73m² in the bexagliflozin group compared to the placebo group
4. Superiority test of the change in HbA1c at week 24 in subjects with eGFR 30 to 44 mL/min/1.73m² in the bexagliflozin group compared to the placebo group

These key secondary endpoints will only be tested sequentially when significant treatment differences are established for the primary efficacy endpoint in the comparisons between the bexagliflozin and placebo groups.

Analysis for key secondary endpoints will be based on the ITT Analysis Set and repeated for the PP Analysis Set.

8.2.1.1. Change in body weight from baseline to week 24 in subjects with a BMI ≥ 25 kg/m²

This will be tested if the change from baseline body weight is significantly different between bexagliflozin and placebo groups based on ITT analysis set for subject with a baseline BMI ≥ 25 kg/m². The comparison of change in body weight between randomized treatments at week 24 will be carried out using similar MMRM ANCOVA model stated in section 8.1.1. Treatment, visit, treatment-by-visit, region, baseline HbA1c level as continuous variable, screening anti-diabetic treatment regimen (insulin treated or other), baseline eGFR (<45 or ≥ 45 mL/min/1.73m²) will be applied as fixed effects. Corresponding baseline weight value will be used as additional covariate. Treatment comparison p-values and difference at week 24 will be estimated from the

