model, with the two-sided 95 % CIs of the treatment difference also presented. If the primary hypothesis is not significant, the nominal p-value will not be used for inferential purposes. The most conservative sensitivity analysis, sensitivity analysis #4 in section 8.1.2, multiple imputations with values after rescue medication considered as missing, will be repeated in ITT analysis set.

8.2.1.2. Change in SBP from baseline to week 24 in subjects with baseline systolic blood pressure \geq 130 mmHg

This will be tested if the primary and the first key secondary efficacy endpoints are significant. Change from baseline in sitting SBP at week 24 will be analyzed using the same MMRM ANCOVA model stated in section 8.1.1. The corresponding baseline SBP value will be used as additional covariate. Treatment comparison p-values and difference at week 24 will be estimated from the model, with the two-sided 95 % CIs of the treatment difference also presented. The most conservative sensitivity analysis, sensitivity analysis #4 in section 8.1.2, multiple imputations with values after rescue medication considered as missing, will be repeated in ITT analysis set.

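### Adding a baseline-by-visit term to the MMRM is a nearly free precision gain at week 24; the model as written is valid but shares one baseline slope across weeks 6, 12 and 24

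*SAP*

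**What the plan says.** The primary MMRM in SAP 8.1.1 has treatment, visit, treatment-by-visit, region, screening insulin use and baseline eGFR category as fixed effects. It then adds: "Baseline HbA1c will be used as covariate". The covariance is unstructured, with AR(1) as fallback, and the tested contrast is the week-24 difference. Protocol 9.5 and the LOCF model in SAP 8.1.2 likewise contain no product of baseline and visit.

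The same structure carries over to the key secondary tests in SAP 8.2.1. For weight, "Corresponding baseline weight value will be used as additional covariate". For blood pressure, "The corresponding baseline SBP value will be used as additional covariate". The two eGFR-group HbA1c tests reuse the 8.1.1 model. Post-baseline HbA1c is analyzed at weeks 6, 12 and 24 (Protocol 9.7; SAP 6.4).

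One part of the plan does allow the slope to vary. The monotone imputation step of sensitivity analyses 1 and 4 fits a separate regression at each time point, with baseline among the predictors.

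**The concern.** A main-effect baseline covariate in a repeated-measures model constrains the slope of change on baseline to be equal at every visit. If the week-24 slope differs from the common fitted slope, baseline is imperfectly adjusted at the one visit that decides the trial, and the residual variance there is larger than it need be.

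Unequal slopes are plausible here. Protocol 6.19 describes HbA1c as averaging roughly three months of glycemia, so a week-6 value still carries much of the pre-treatment period while a week-24 value does not. The SAP's week-6 window (days 1 to 63, with unscheduled and early-termination samples mapped in) can bring in still earlier values. At stake is precision for the primary contrast and, with less power in reserve, for the eGFR-group HbA1c tests.

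**Working it through.** **1. The plan's own figure.** SAP 3.7 plans "an estimated sample size of 133 evaluable subjects per treatment arm", which "yields approximately 90% power to detect a treatment difference", "based on a two group t-test with a two-sided significance at the 5% level". The inputs are a difference of 0.4% and an SD of change of 1.0%. The normal formula gives 2 × (1.960 + 1.282)² × 1.0² / 0.4² = 131.3, so 132 per arm. Exact t-test power is 90.15% at 133 and 89.9% at 132. The figure reproduces. With 12% dropout, 150 × 0.88 = 132. The SD of 1.0% is that of the raw change, so planned power takes no credit for baseline adjustment.

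**2. Formula for the loss.** Let s be the true slopes at weeks 6, 12 and 24, V the residual covariance and v the baseline variance. With complete data and unstructured covariance, the common slope is b = w's, with w = V⁻¹1 / (1'V⁻¹1). The week-24 variance is then too large by the fraction v × (s₂₄ − b)² / V₂₄.

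**3. Assumed inputs (none is in the documents).** Residual SDs 0.5/0.7/0.9, so V₂₄ = 0.81. Baseline SD 0.85, so v = 0.7225. The correlation is equal between all visits and runs from 0.3 to 0.8. Slopes change linearly, so week 12 lies midway.

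**4. One case in full.** At correlation 0.6 the weights are 0.921, 0.164 and −0.085. For slopes −0.15/−0.25/−0.35, b = −0.1382 − 0.0410 + 0.0298 = −0.1494. The excess is 0.7225 × (−0.35 + 0.1494)² / 0.81 = 0.7225 × 0.04024 / 0.81 = 3.6%.

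**5. Range of week-24 variance excess.**

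| Slopes, week 6 to week 24 | Corr. 0.3 | Corr. 0.6 | Corr. 0.8 | Equal visit SDs (0.8) |
|---|---|---|---|---|
| all equal | 0 | 0 | 0 | 0 |
| −0.20 to −0.30 | 0.6% | 0.9% | 1.5% | 0.3% |
| −0.15 to −0.35 | 2.3% | 3.6% | 6.2% | 1.1% |
| −0.10 to −0.40 | 5.1% | 8.1% | 13.9% | 2.5% |

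The largest entry, 13.9%, is √1.139 − 1 = 6.7% on the standard error.

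**6. Primary power.** A second set of assumptions fixed the raw week-24 SD of change at the planned 1.0%, with baseline SD 0.9 and slopes −0.15/−0.30/−0.45. By normal approximation, power at 132 per arm was 92.7% with the common slope and 94.5% with visit-specific slopes. Over slope differences of 0 to 0.4 the gain was 0 to 3.9 points, and the common-slope model never fell below 91%.

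**7. Simulation check.** Fitted unstructured models, 300 subjects, about 12% monotone dropout (MCAR and MAR), 1,500 runs per scenario, no Kenward-Roger adjustment. The ratio of the common-slope to the visit-specific standard error was 0.999 for slope difference 0, 1.016-1.018 for 0.2, 1.040-1.043 for 0.3 and 1.073-1.078 for 0.4. Common-slope mean estimates lay between −0.398 and −0.406 for a true −0.4. Type I error was 5.0% in the one null scenario run.

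**8. eGFR-group tests.** With 135 per group (SAP 3.5, by screening eGFR), 135 × 0.88 / 2 ≈ 59 per arm. Taking the planning values as the common-slope case, 0.4 / √(2/59) = 2.173 and power is Φ(2.173 − 1.960) = 58.4%. Removing a 3.6% excess gives Φ(2.173 × √1.036 − 1.960) = 59.9%; removing 8.1% gives 61.7%. The gain is about 1.5 to 3.3 points.

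**9. Price of the term.** Two parameters. The critical t at 250 df moves from 1.96950 to 1.96958, and with equal slopes the simulated standard error rises by about 0.1%.

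**The case against.** The strongest case against is that nothing here is wrong. A main-effect baseline covariate in a pre-specified MMRM with unstructured covariance and Kenward-Roger degrees of freedom is a legitimate choice. That stands, and it limits the point to an efficiency suggestion.

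A reader might infer several stronger things that the documents do not support:

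- *That precision is certainly lost.* It is lost only if slopes differ. The documents give no slopes, and the three-month argument makes a difference plausible without giving its size.
- *That unstructured covariance always ties the common slope to week 6.* That follows from assuming week 6 is the least variable visit. With equal SDs and equal correlations each visit has weight one-third, and the loss shrinks to the last column of the table. Under the AR(1) fallback the weights would differ again.
- *That dropouts are handled with a wrong slope and the estimate is biased.* The MCAR and MAR simulations showed no material bias, and the imputation regressions in SAP 8.1.2 already let the baseline coefficient change by visit.
- *That the trial is underpowered because of this.* Primary power stayed above the planned 90% in every scenario.
- *That a loss has been shown for weight and SBP.* No figure was computed for them; the argument there is by structure only.

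Finally, the SAS code (Attachment 4) is not in the reviewed text and may already contain the term. If so, the SAP wording should say so.

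**Conclusion.** The point holds as a low-cost improvement, not as an error. As written, the HbA1c, weight and SBP models share one baseline slope over three visits while testing only the last. The loss in week-24 variance is zero with equal slopes. It is 0.3-2.5% with equal visit SDs over the slope patterns tried, and 0.6-13.9% when variability is assumed to grow from 0.5 to 0.9 with correlations of 0.3 to 0.8. Every one of these figures rests on assumed slopes, SDs and correlations. Validity and planned primary power are not in question. Because the term costs about 0.1% of the standard error when it is not needed, the balance favors including it.

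**What to change.** Before unblinding:

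- Add baseline HbA1c-by-visit to the MMRM in SAP 8.1.1, to the analysis-stage MMRMs of the sensitivity analyses in 8.1.2 and to the eGFR-group HbA1c models in 8.2.1.3. The imputation regressions need no change on this account.
- Add baseline weight-by-visit to 8.2.1.1 and baseline SBP-by-visit to 8.2.1.2.
- Check that Attachment 4 specifies the same models, and record the addition in SAP section 13 as a change from Protocol 9.5 and 9.6.

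The cost is two parameters and one line of code per model. No extra subjects or data are needed.

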9.5 Analysis of Efficacy

All efficacy analyses will be performed based on the ITT analysis set. The primary endpoint analysis will also be conducted using the PP Analysis Set (if deemed different from ITT analysis set).

For the primary endpoint of HbA1c change from baseline over 24 weeks of treatment, the MMRM analysis of covariance model (ANCOVA) with baseline HbA1c as a covariate will be fitted to the available data, incorporating all visits at which HbA1c was measured for each subject including the scheduled and the unscheduled visits for measurement of HbA1c (National Research Council, 2010). Treatment, visit, treatment-by-visit, and stratification factors for randomization (HbA1c level [7.0 to 8.5% or 8.6 to 10.5%], screening anti-diabetic treatment regimen [insulin treated, other], eGFR [30-44 or 45-59 mL/min/1.73m²]) will be applied as fixed effects. From this model, an estimate of the treatment difference at week 24 will be generated, as will an assessment of whether this estimate is significantly different when comparing at a two-sided 0.05 level of significance. An unstructured within-patient covariance structure will be assumed. If the model with the unstructured covariance structure does not converge, an autoregressive(1) covariance structure will be used. HbA1c values obtained after the start of rescue medication will not be excluded from this primary analysis.

The MMRM model is one approach to obtain treatment effect estimates in the presence of missing data. As sensitivity analyses for missing data, the following will be performed:

- 1) Missing HbA1c data will be imputed via multiple imputation (MI), following which the MMRM will be repeated on the complete datasets with results combined across complete datasets using standard MI techniques; HbA1c values collected after the start of rescue medication will not be considered missing.
- 2) Missing HbA1c data will be imputed via LOCF, following which the MMRM will be repeated; HbA1c values collected after the start of rescue medication will be considered missing.
- 3) HbA1c values collected after the start of rescue medication will be considered missing, and the MMRM analyses will be re-performed.

If it is deemed that the PP analysis set is different from the ITT analysis set, same analyses as described above will be conducted in PP analysis set as well.

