9.7 Other Efficacy Analyses

Changes in HbA1c, FPG, SBP/DBP, body weight, and albumin level in urine for all subjects during the treatment period will be summarized descriptively by each time point (i.e., Weeks 6, 12, 24). In addition, these endpoints may be analyzed using a similar MMRM model as used for the primary analysis of HbA1c to compare bexagliflozin with placebo.

Cumulative summary on the proportion of subjects achieving HbA1c < 7%, and the proportion of subjects achieving body weight reduction of at least 5% will also be presented.

Analyses will be conducted using ITT analysis set.

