6. GENERAL ASPECTS FOR STATISTICAL ANALYSIS

6.1. GENERAL METHODS

Statistical methodology and analyses are in accordance with the principles outlined by the ICH E9 guidelines. All statistical analyses will be conducted using SAS statistical software version 9.3 or higher.

Tables, listings and figures (TLFs) will be produced in accordance with the principles outlined by the ICH E3 guidelines. For most summary statistics, data will be analyzed by the following treatment groups: Bexagliflozin 20 mg and Placebo. All available data will be presented in the subject listings.

Data summaries will use descriptive statistics (number of subjects [n], mean, standard deviation [SD], Q1, median, Q3, minimum, and maximum) for continuous variables, and frequency and percentage of subjects for categorical and ordinal variables, unless otherwise specified.

Unless otherwise specified, all tests will be two-sided using a 0.05 level of significance. All confidence intervals (CIs) will be two-sided 95% CIs.

The analysis visit window will be assigned to data collection. One selected data point per visit will appear in summary tables and figures. Refer to section 6.4 for details. All visit assessment data will be included in shift tables and will appear in the subject listings.

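### The only fallback for the primary MMRM is AR(1), whose single variance across visits could misstate the week-24 standard error; the trigger is unlikely, and a better fallback costs almost nothing.

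*SAP*

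**What the plan says.** SAP 8.1.1 fits an MMRM to the change in HbA1c with an unstructured within-subject covariance and Kenward-Roger degrees of freedom, and tests the treatment difference at week 24. Its contingency rule is: "If the model with the unstructured covariance structure does not converge, an autoregressive (1) covariance structure will be used". Protocol 9.5 has the same rule: "If the model with the unstructured covariance structure does not converge, an autoregressive(1) covariance structure will be used". Neither document names an intermediate structure or a robust (sandwich) variance.

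Protocol 9.7 lists the on-treatment time points as "i.e., Weeks 6, 12, 24". SAP 6.4 maps every post-baseline record, unscheduled ones included, to one of three windows and keeps one record per window.

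The model is reused. SAP 8.2.1.2 (systolic blood pressure) and 8.2.1.3 (HbA1c by eGFR group) take over the 8.1.1 model, and 8.2.1.1 (body weight) uses a similar one. All are in the hierarchical testing sequence. Multiple-imputation sensitivity analyses 1 and 4 refit the primary model in each imputed dataset.

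The only variability figure is in SAP 3.7: "The pooled standard deviation for the change from baseline to Week 24 in HbA1c for the active and placebo groups will be 1.0" (percent). No SD is given for week 6 or week 12, and no between-visit correlation.

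**The concern.** The hypothesis concerns week 24 only. An unstructured covariance estimates a separate week-24 variance. Plain AR(1) estimates one variance for all visits and one correlation parameter, so the week-24 standard error depends on how variable HbA1c change is at weeks 6 and 12. If those visits are less variable, the interval is too narrow and the test rejects too often. If they are more variable, the test is conservative and loses power. Kenward-Roger is a small-sample adjustment made within the assumed covariance model, so it does not repair a wrong one.

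The documents give some reason to doubt equal variances. Protocol 6.19 says HbA1c reflects roughly three months of glycemia, and Protocol 3.2.2 says a stable HbA1c baseline takes 12 weeks. At week 6 the value still partly reflects the time before randomization, so a smaller spread of change than at week 24 is plausible. It is not shown.

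At stake is the validity of the confirmatory week-24 test in the one situation the fallback exists for, and of the secondary tests that copy it. Choosing a better structure after seeing an AR(1) result would be post hoc.

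**Working it through.** **1. Inputs from the documents.** SAP 6.1: "all tests will be two-sided using a 0.05 level of significance". SAP 3.7: "The placebo-corrected population mean change from baseline to Week 24 in HbA1c in the dose group of 20 mg will be -0.4" (percent); week-24 SD 1.0%; "133 evaluable subjects per treatment arm yields approximately 90% power to detect a treatment difference"; "Approximately 300 subjects will be randomized and equally allocated"; 12% dropout. Visits at weeks 6, 12 and 24.

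**2. The plan's own figure.** n per arm = 2 × (1.960 + 1.282)² × 1.0² / 0.4² = 131.4, so 132 by the normal approximation. Power at 133 per arm is 90.4% (normal) or 90.1% (t-test). The stated figure reproduces.

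**3. Assumptions.** SDs at weeks 6 and 12, expressed relative to week 24 = 1.0, and all correlations. Four correlation patterns were used: AR(1) with 0.7 between adjacent visits; decay in actual weeks at 0.8 or at 0.9 per six weeks; and compound symmetry at 0.6. Dropout is completely at random and both arms share one covariance.

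**4. Formula.** With ratio r = (SE reported under AR(1)) / (true SE), the real size of a nominal 5% test is 2 × [1 − Φ(1.96 r)].

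With complete data, the best-fitting AR(1) variance is close to the mean of the three visit variances, so r ≈ √[(s₆² + s₁₂² + s₂₄²)/3] when s₂₄ = 1. For SDs 0.8/0.9/1.0: (0.64 + 0.81 + 1.00)/3 = 0.817; r = 0.904; 1.96 × 0.904 = 1.771; size = 0.0765. The full AR(1) fits give ratios within 0.005 of this shortcut for every pattern tabulated.

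**5. Results.** The fourth column is the large-sample AR(1) fit with 12% dropout over the four correlation patterns. The last column is simulated REML AR(1) fits: 150 per arm, 12% dropout, correlation 0.8 per six weeks, 4,000 runs, t reference with 290 df in place of Kenward-Roger, Monte Carlo SE about 0.003 to 0.005.

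| SDs at weeks 6/12/24 | r (shortcut) | Size (shortcut) | Size, 12% dropout | Size, simulated |
|---|---|---|---|---|
| 1.0/1.0/1.0 | 1.000 | 0.0500 | 0.049–0.051 | 0.051 |
| 0.9/0.95/1.0 | 0.951 | 0.0624 | 0.062–0.064 | not run |
| 0.8/0.9/1.0 | 0.904 | 0.0765 | 0.077–0.078 | 0.072 |
| 0.7/0.85/1.0 | 0.859 | 0.0923 | 0.093–0.095 | 0.094 |
| 0.6/0.8/1.0 | 0.816 | 0.1095 | 0.111–0.112 | 0.118 |
| 1.2/1.1/1.0 | 1.103 | 0.0306 | 0.029–0.031 | 0.027 |

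In this large-sample calculation r does not depend on sample size, so more subjects do not cure the problem.

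**6. What this does to the interval.** At 133 per arm the correct 95% half-width is 1.96 × √(2/133) × 1.0 = 0.240. With SDs 0.8/0.9/1.0, AR(1) would report 0.240 × 0.904 = 0.217.

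**7. Spacing.** The first row isolates it. Variances are equal, the correlation patterns include decay over the true 6- and 12-week gaps, and the size stays at 0.049 to 0.051.

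**8. The alternatives.** Heterogeneous Toeplitz, heterogeneous AR(1) and heterogeneous compound symmetry, fitted with model-based standard errors to the same kind of assumed covariances with 12% dropout, give a size of about 0.04 to 0.05 whether the SD rises, stays flat or falls.

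**9. The trigger.** Three visits need six covariance parameters. Unstructured REML fits to simulated normal data (SDs 0.7/0.85/1.0, 12% dropout, baseline plus four binary covariates) converged in 100 of 100 runs at each of 300, 135 and 60 subjects, with moderate and with very high between-visit correlation. This was not run in SAS.

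**The case against.** - **The rule is conditional and the condition is remote.** This stands. Suppose non-convergence occurred in 1% of trials, independently of the result. Even the worst pattern tabulated would give an overall type I error of 0.99 × 0.05 + 0.01 × 0.112 = 0.0506. At 5% it would be 0.95 × 0.05 + 0.05 × 0.112 = 0.053. Both non-convergence rates are assumptions. A reader might expect the eGFR subsets to reach the fallback, but at least 135 subjects are planned per group (by screening eGFR; the analysis groups use baseline eGFR), and the convergence check gives no sign of it.
- **The direction is not established.** This also stands. A reader might infer that the fallback would inflate the type I error. The documents support only that it could. With one SD given, a falling pattern, under which the test is conservative, cannot be excluded.
- **Unequal spacing.** A reader might blame the 6- and 12-week gaps, since plain AR(1) treats them as equal. The check does not support this: with equal variances the size is essentially nominal.
- **The exact SAS option is unseen.** The sample code is in an attachment to SAP 21.2 that is not available here. If it specifies a heterogeneous AR(1), the point reduces to stating that in the text. Homogeneous AR(1) is the ordinary reading of the words.
- **Heterogeneous Toeplitz has five parameters against six,** so it gives little relief if the unstructured fit fails. This is fair, and is why a four-parameter structure should follow it.

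What remains is that the plan drops from six covariance parameters straight to two and gives up the week-24 variance, when structures in between keep it.

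**Conclusion.** The point holds as an inexpensive improvement with low practical impact. It is not evidence that the planned primary test is invalid: the unstructured model is sound and will very probably be the one used.

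If AR(1) were used, the week-24 test at a nominal 5% would have a type I error of about 6% to 11% for a week-6 SD between 0.9 and 0.6 of the week-24 SD, about 5% for equal SDs, and about 3% for SDs of 1.2/1.1/1.0. These figures rest on the homogeneous reading of AR(1), on assumed SDs at weeks 6 and 12 and assumed correlations, on the same covariance in both arms, and on dropout completely at random. Dropout that depends on observed HbA1c could add bias under a wrong covariance and was not computed.

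**What to change.** In SAP 8.1.1, replace the AR(1) sentence with a fixed sequence, taking the first structure that converges: unstructured; heterogeneous Toeplitz; then one named four-parameter structure, either heterogeneous AR(1) or heterogeneous compound symmetry. Keep Kenward-Roger throughout. Apply the same sequence to every model that copies 8.1.1 (body weight, systolic blood pressure, the eGFR groups, the exploratory MMRMs and the refits to imputed data), and match the sample code to it. Record the change from Protocol 9.5 in SAP section 13, before unblinding.

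Sandwich standard errors are optional. If they are adopted, the SAP must also name the degrees-of-freedom method that goes with them, because Kenward-Roger adjusts the model-based variance.

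The cost is a few sentences and a few lines of code. The downside is a few more covariance parameters than AR(1) (four or five against two). Results do not change if the unstructured model converges.
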